### **11.2 Database management and quality control**

Novartis personnel (or designated CRO) will review the data entered by investigational staff for completeness and accuracy. Electronic data queries stating the nature of the problem and requesting clarification will be created for discrepancies and missing values and sent to the investigational site via the EDC system. Designated investigator study staff are required to respond promptly to queries and to make any necessary changes to the data.

Concomitant treatments and prior medications entered into the database will be coded using the WHO Drug Reference List, which employs the Anatomical Therapeutic Chemical classification system. Medical history/current medical conditions and adverse events will be coded using the Medical dictionary for regulatory activities (MedDRA) terminology.

Randomization codes and data about all study treatment(s) dispensed to the patient will be tracked using an Interactive Response Technology (IRT). The system will be supplied by a vendor, who will also manage the database. The data will be sent electronically to Novartis (or a designated CRO) at specific timelines.

Each occurrence of a code break via IRT will be reported to the clinical team and monitor. The code break functionality will remain available until study shut down or upon request of Novartis.

Commercially Confidential Information

### **11.3 Site monitoring**

Before study initiation, at a site initiation visit, virtual training event, or at an investigator's meeting, a Novartis delegated CRO representative will review the protocol and data capture requirements (i.e. eCRFs) with the investigators and their staff. During the study, Novartis employs several methods of ensuring protocol and GCP compliance and the quality/integrity of the sites' data. The field monitor will check the completeness of patient records, the accuracy of data capture / data entry, the adherence to the protocol and to Good Clinical Practice, the progress of enrollment, and to ensure that study treatment is being stored, dispensed, and accounted for according to specifications. Key study personnel must be available to assist the field monitor during these visits. Continuous remote monitoring of each site's data may be performed by a centralized Novartis delegated CRO/CRA organization. Additionally, a central analytics organization may analyze data to identify risks and trends for site operational parameters, and provide reports to Novartis clinical teams to assist with trial oversight.

The investigator must maintain source documents for each patient in the study, consisting of case and visit notes (hospital or clinic medical records) containing demographic and medical information, laboratory data, electrocardiograms, and the results of any other tests or assessments. All information on CRFs must be traceable to these source documents in the patient's file. Data not requiring a separate written record will be defined before study start and will be recorded directly on the CRFs. The investigator must also keep the original informed consent form signed by the patient (a signed copy is given to the patient).

The investigator must give the monitor access to all relevant source documents to confirm their consistency with the data capture and/or data entry. Novartis monitoring standards require full verification for the presence of informed consent, adherence to the inclusion/exclusion criteria, documentation of SAEs, and of data that will be used for all primary variables. Additional checks of the consistency of the source data with the CRFs are performed according to the study-specific monitoring plan. No information in source documents about the identity of the patients will be disclosed.

## **12 Data analysis and statistical methods**

Any data analysis carried out independently by the investigator should be submitted to Novartis before publication or presentation.

## **12.1 Analysis sets**

For all analysis sets, patients will be analyzed according to the study treatment received.

The safety analysis set will include all patients who received any study drug.

The PK analysis set will include all patients with at least one available valid (i.e. not flagged for exclusion) PK concentration measurement, who received any study drug and with no protocol deviations that impact PK data.

The PD analysis set will include all patients with available PD data and no protocol deviations with relevant impact on PD data.

Protocol deviation impact will be documented appropriately and assessed by the Sponsor study team, including the Medical and Study Leads with input from of the trial team.

## **12.2 Patient demographics and other baseline characteristics**

Demographic and other baseline data including disease characteristics will be listed and summarized descriptively by treatment group for the Safety set.

Categorical data will be presented as frequencies and percentages. For continuous data, mean, standard deviation, median, minimum, and maximum will be presented. For selected parameters, 25th and 75th percentiles may also be presented.

Relevant medical histories and current medical conditions at baseline will be listed by treatment group, system organ class and preferred term.

## **12.3 Treatments**

Concomitant medications and significant non-drug therapies prior to and after the start of the study treatment will be listed by treatment group according to the WHO Drug Reference List, which employs the Anatomical Therapeutic Chemical classification system.

## **12.4 Analysis of the primary endpoint(s)**

The primary objective of this study is to assess the safety and tolerability of nidufexor as well as the efficacy of nidufexor on albuminuria in patients with diabetic nephropathy during 24 weeks of treatment.

### **12.4.1 Definition of primary endpoint(s)**

For analytical purposes, all safety data, including laboratory measurements, vital signs, adverse events, ECG, are considered primary endpoints.

For efficacy evaluation, log-transformed ratios to baseline UACR and 24-hour urine albumin excretion at Week 24 are the primary endpoints.

### **12.4.2 Statistical model, hypothesis, and method of analysis**

#### **12.4.2.1 Safety endpoints**

For all safety analyses, the safety set will be used. Safety and tolerability data will be summarized. Formal statistical analysis will not be performed on the safety and tolerability data.

## **Adverse events**

All information obtained on AEs will be displayed by treatment group and patient.

The number (and percentage) of patients with treatment emergent adverse events (events started after the first dose of study medication or events present prior to start of treatment but increased in severity based on preferred term) will be summarized in the following ways:

- by treatment, primary system organ class and preferred term.
- by treatment, primary system organ class, preferred term and maximum CTCAE grade

Separate summaries will be provided for study medication related AEs, death, SAEs, other significant AEs and AEs leading to discontinuation.

A patient with multiple AEs within a primary system organ class is only counted once towards the total of the primary system organ class.

## **Vital signs**

All vital signs data will be listed by treatment group, patient, and visit/time and if ranges are available, abnormalities (and relevant orthostatic changes) will be flagged. Summary statistics will be provided by treatment and visit/time.

## **12-lead ECG**

All ECG data will be listed by treatment group, patient and visit/time, abnormalities will be flagged. Summary statistics will be provided by treatment and visit/time.

## **Clinical laboratory evaluations**

All laboratory data will be listed by treatment group, patient, and visit/time and abnormalities will be flagged. Summary statistics will be provided by treatment and visit/time.

### **12.4.2.2 Efficacy and/or Pharmacodynamic Endpoints**

For all efficacy PD analyses, the PD set will be used.

A repeated measures Analysis of Covariance (ANCOVA) will be performed for log-transformed ratio to baseline UACR measured at each visit. The model will include effects for log-transformed baseline, treatment, visit, treatment by visit interaction and visit by log-transformed baseline interaction. An unstructured variance-covariance matrix will be used to account for correlation among multiple measurements from the same patient and variance heterogeneity.

Similarly an ANCOVA with treatment as the classification factor and log-transformed baseline as the covariate will be conducted for log-transformed ratio to baseline 24-hour urine albumin excretion.

Point estimates, the associated confidence intervals as well as the p-values for treatment difference at each visit will be provided within the ANCOVA framework. The null hypothesis of no treatment difference in UACR or 24-hour urine albumin excretion will be tested at the one-sided 0.1 significance level. A treatment difference of at least 25% in favor of nidufexor will be considered clinically significant.

### **12.4.3 Handling of missing values/censoring/discontinuations**

Missing data will not be imputed.

Assuming missing at random, a patient with missing value at a visit will still contribute to the estimation of the treatment effect at that particular visit as the likelihood-based repeated measures ANCOVA borrows information from non-missing values of this patient and other patients.

### **12.4.4 Sensitivity and Supportive analyses**

Commercially Confidential Information

## **12.5 Analysis of secondary endpoints**

### **12.5.1 Efficacy and/or Pharmacodynamic endpoint(s)**

Log-transformed ratio to baseline for eGFR, free water clearance, HbA1c and fasting lipid profiles (total cholesterol, HDL, LDL, triglycerides and Lp(a)) as well as change from baseline in weight, BMI and WTH ratio will be analyzed using the same repeated measures ANCOVA described in [Section 12.4.2](#) with baseline in lieu of log-transformed baseline as a covariate for change from baseline analysis. For parameters with only one post-treatment measurement an ANCOVA with treatment as a classification factor and baseline (or log-transformed baseline if applicable) as a covariate will be employed.

### **12.5.2 Pharmacokinetics**

Nidufexor plasma concentration data will be listed by patient and visit/sampling time point. Descriptive summary statistics will be provided by visit/sampling time point, including the frequency (n, %) of concentrations below the LLOQ and reported as zero.

Summary statistics will include mean (arithmetic and geometric), SD, CV (arithmetic and geometric), median, minimum and maximum. An exception to this is Tmax where median, minimum and maximum will be presented. Concentrations below LLOQ will be treated as zero in summary statistics and for PK parameter calculations. A geometric mean will not be reported if the dataset includes zero values. Pharmacokinetic parameters will be calculated as described in [Section 8.5.2](#) and will be listed by patient.

For standard pharmacokinetic abbreviations and definitions see the list provided at the beginning of this protocol.

The following pharmacokinetic parameters will be determined using the actual recorded sampling times and non-compartmental method(s) with Phoenix WinNonlin (Version 6.2 or higher): Cmax, Tmax, and AUClast from the plasma concentration-time data. The linear trapezoidal rule will be used for AUC calculation.

Commercially Confidential Information

#### **12.5.5 PK/PD relationships**

The relationship between key efficacy/PD parameters (including, but not limited to UACR, 24-hour urine albumin excretion and eGFR and nidufexor PK parameters (Cmax and AUC0-6) may be explored using a graphical approach and descriptive statistics may be provided. Additional statistical analysis such as regression may be performed, if necessary. Modeling approach may also be used to explore the PK/PD interactions.

#### **12.5.6 Patient reported outcomes**

Change from baseline itch VAS measurements will be analyzed using the same repeated measures ANCOVA described in [Section 12.4.2](#).

Commercially Confidential Information

## 12.7 Interim analyses

Commercially Confidential Information

## 12.8 Sample size calculation

### 12.8.1 Primary endpoint(s)

Data from 50 patients per arm will provide 72% power to detect the combination of a drug effect on UACR at Week 24 that is both clinically significant (defined as an estimated relative reduction of at least 25% compared to placebo) and statistically significant (defined as  $\geq 90\%$  probability of a  $> 0\%$  reduction relative to placebo) if the true placebo adjusted reduction is 30%. The figure below shows the probability of decision making for various true drug effects at a sample size of 50 patients per arm. A “Go” decision will be made if both the clinical significance and the statistical significance criteria are met while a “No Go” decision will be made if neither the clinical significance nor the statistical significance criterion is met. Otherwise it will be an indeterminate situation requiring further information to be obtained before a decision can be made.

The power calculations were performed using simulations based on log-transformed ratio to baseline analysis. The standard deviation was assumed to be 0.6, estimated from published studies in the literature ([Hanes et al 2018](#)). Treatment comparison was based on a one-sided two sample t-test.

Commercially Confidential Information

## **13 Ethical considerations and administrative procedures**

### **13.1 Regulatory and ethical compliance**

This clinical study was designed and shall be implemented, executed and reported in accordance with the ICH Harmonized Tripartite Guidelines for Good Clinical Practice, with applicable local regulations (including European Directive 2001/20/EC, US CFR 21), and with the ethical principles laid down in the Declaration of Helsinki.

### **13.2 Responsibilities of the investigator and IRB/IEC**

Before initiating a trial, the investigator/institution must obtain approval/favorable opinion from the Institutional Review Board/Independent Ethics Committee (IRB/IEC) for the trial protocol, written informed consent form, consent form updates, patient recruitment procedures (e.g., advertisements) and any other written information to be provided to patients. Prior to study start, the investigator is required to sign a protocol signature page confirming his/her agreement to conduct the study in accordance with these documents and all of the instructions and procedures found in this protocol and to give access to all relevant data and records to Novartis monitors, auditors, Novartis Quality Assurance representatives, designated agents of Novartis, IRBs/IECs, and regulatory authorities as required.

**If an inspection of the clinical site is requested by a regulatory authority, the investigator must inform Novartis immediately that this request has been made.**

### **13.3 Publication of study protocol and results**

The protocol will be registered in a publicly accessible databases such as clinicaltrials.gov and as required in EudraCT and/or as required by local country registries. In addition, after study completion (*defined as last patient last visit*) and finalization of the study report the results of this trial will be submitted for publication and posted in a publicly accessible database of clinical trial results, such as the Novartis clinical trial results website and all required Health Authority websites (e.g. Clinicaltrials.gov, EudraCT etc.).

For details on the Novartis publication policy including authorship criteria, please refer to the Novartis publication policy training materials that were provided to you at the trial investigator meetings

### **13.4 Quality Control and Quality Assurance**

Novartis maintains a robust Quality Management System (QMS) that includes all activities involved in quality assurance and quality control, to ensure compliance with written Standard Operating Procedures as well as applicable global/local GCP regulations and ICH Guidelines.

Audits of investigator sites, vendors, and Novartis systems are performed by auditors, independent from those involved in conducting, monitoring or performing quality control of the clinical trial. The clinical audit process uses a knowledge/risk based approach.

Audits are conducted to assess GCP compliance with global and local regulatory requirements, protocols and internal SOPs, and are performed according to written Novartis processes

## **14 Protocol adherence**

This protocol defines the study objectives, the study procedures and the data to be collected on study participants. Additional assessments required to ensure safety of patients should be administered as deemed necessary on a case-by-case basis. **Under no circumstances including incidental collection is an investigator allowed to collect additional data or conduct any additional procedures for any purpose involving any investigational drugs under the protocol, other than the purpose of the study.** If despite this interdiction prohibition, data, information, observation would be incidentally collected, the investigator shall immediately disclose it to Novartis and not use it for any purpose other than the study, except for the appropriate monitoring on study participants.

Investigators will apply due diligence to avoid protocol deviations. If an investigator feels a protocol deviation would improve the conduct of the study this must be considered a protocol amendment, and unless such an amendment is agreed upon by Novartis and approved by the IRB/IEC and health authorities, where required, it cannot be implemented.

## **14.1 Protocol Amendments**

Any change or addition to the protocol can only be made in a written protocol amendment that must be approved by Novartis, health authorities where required, and the IRB/IEC prior to implementation.

Only amendments that are required for patient safety may be implemented immediately provided the health authorities are subsequently notified by protocol amendment and the reviewing IRB/IEC is notified.

Notwithstanding the need for approval of formal protocol amendments, the investigator is expected to take any immediate action required for the safety of any patient included in this study, even if this action represents a deviation from the protocol. In such cases, Novartis should be notified of this action and the IRB/IEC at the study site should be informed according to local regulations.

## **16 Appendices**

### **16.1 Appendix 1: Clinically notable laboratory values and vital signs**

Please refer to the Central Laboratory Manual for a list of clinically significant laboratory values.

## 16.2 Appendix 2: Liver event and Laboratory trigger Definitions and Follow-up Requirements

**Table 16-1 Liver Event and Laboratory Trigger Definitions**

	Definition/ threshold
LIVER LABORATORY TRIGGERS	

• <math>3 \times \text{ULN} < \text{ALT} / \text{AST} \leq 5 \times \text{ULN}</math>

• <math>1.5 \times \text{ULN} < \text{TBL} \leq 2 \text{ULN}</math>

LIVER EVENTS	

• <math>\text{ALT or AST} > 5 \times \text{ULN}</math>

• <math>\text{ALP} > 2 \times \text{ULN}</math> (in the absence of known bone pathology)

• <math>\text{TBL} > 2 \times \text{ULN}</math> (in the absence of known Gilbert syndrome)

• Potential Hy's Law cases (defined as <math>\text{ALT or AST} > 3 \times \text{ULN}</math> and <math>\text{TBL} > 2 \times \text{ULN}</math> [mainly conjugated fraction] without notable increase in ALP to <math>> 2 \times \text{ULN}</math>)

• Any clinical event of jaundice (or equivalent term)

• <math>\text{ALT or AST} > 3 \times \text{ULN}</math> accompanied by (general) malaise, fatigue, abdominal pain, nausea, or vomiting, or rash with eosinophilia

• Any adverse event potentially indicative of a liver toxicity*

\*These events cover the following: hepatic failure, fibrosis and cirrhosis, and other liver damage-related conditions; the non-infectious hepatitis; the benign, malignant and unspecified liver neoplasms TBL: total bilirubin; ULN: upper limit of normal

[Chalasani and Regev 2016](#)

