#### 8.4.3.3 Liver function tests

Alanine aminotransferase (ALT), aspartate aminotransferase (AST), total bilirubin (TBL), serum albumin (Alb), prothrombin time (PT)/ international normalized ratio (INR), alkaline phosphatase (ALP), gamma-glutamyl transferase (γGT)

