## 10.2 Additional Safety Monitoring

### 10.2.1 Liver safety monitoring

To ensure patient safety and enhance reliability in determining the hepatotoxic potential of an investigational drug, a standardized process for identification, monitoring and evaluation of liver events has to be followed.

Please refer to [Section 16.2](#) in [Appendix 2](#) for complete definitions of liver laboratory triggers and liver events.

Once a participant has been exposed to study treatment, every liver event defined in [Section 16.2](#) should be followed up by the investigator or designated personnel, as summarized below. Additional details on actions required in case of liver events are outlined in [Section 16.2](#). Repeat liver chemistry tests (ALT, AST, TBL, Direct Bilirubin, PT/INR, ALP and  $\gamma$ -GT) to confirm elevation.

- These liver chemistry repeats will be performed using the central laboratory. If results will not be promptly available from the central laboratory, then the repeats can also be performed at a local laboratory to monitor the safety of the patient. If a liver event is subsequently reported, any local liver chemistry tests previously conducted that are associated with this event should have results recorded on the appropriate CRF
- If the initial elevation is confirmed, close observation of the patient will be initiated, including consideration of treatment interruption if deemed appropriate.
- Discontinuation of the investigational drug (refer to the discontinuation of study treatment information located in [Section 9](#)), if appropriate
- Hospitalization of the patient if appropriate
- Causality assessment of the liver event
- Thorough follow-up of the liver event
  - These investigations can include based on investigator’s discretion: serology tests, imaging and pathology assessments, hepatologist’s consultancy
- Obtaining a more detailed history of symptoms and prior or concurrent diseases.

- Obtaining a history of concomitant drug use (including nonprescription medications and herbal and dietary supplement preparations), alcohol use, recreational drug use, and special diets.
- Exclusion of underlying liver disease.
- Obtaining a history of exposure to environmental chemical agents.
- Considering gastroenterology or hepatology consultations.

All follow-up information, and the procedures performed must be recorded as appropriate in the liver event CRF.

Refer to the Site Operations Manual for additional details.

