**Table 16-2 Follow Up Requirements for Liver Events and Laboratory Triggers**

Criteria	Actions required	Follow-up monitoring
Potential Hy's Law case a	
 
Discontinue the study treatment immediately
 
Hospitalize, if clinically appropriate
 
Establish causality
 
Complete liver CRF
 
	ALT, AST, TBL, Alb, PT/INR, ALP and $\gamma$ -GT until resolution c (frequency at investigator discretion)
ALT or AST		
for patients with normal baseline: $> 8 \times$ ULN For patients with elevated baseline $> 8 \times$ ULN or $> 500$ U/L whichever comes first	
 
Discontinue the study treatment immediately
 
Hospitalize if clinically appropriate
 
Establish causality
 
Complete liver CRF
 
	ALT, AST, TBL, Alb, PT/INR, ALP and $\gamma$ GT until resolution c (frequency at investigator discretion)
For patients with normal baseline: $> 5$ to $\leq 8 \times$ ULN For patients with elevated baseline: $>5$ to $\leq 8 \times$ ULN or $>5X$ ULN to $\leq 500$ U/L whichever comes first	
 
Repeat LFT within 48 hours
 
If elevation persists, continue follow-up monitoring
 
If elevation persists for more than 2 weeks, discontinue the study drug
 
Establish causality
 
Complete liver CRF
 
	ALT, AST, TBL, Alb, PT/INR, ALP and $\gamma$ GT until resolution c (frequency at investigator discretion)
$> 3 \times$ ULN accompanied by symptoms b	
 
Discontinue the study treatment immediately
 
Hospitalize if clinically appropriate
 
Establish causality
 
Complete liver CRF
 
	ALT, AST, TBL, Alb, PT/INR, ALP and $\gamma$ GT until resolution c (frequency at investigator discretion)
$> 3$ to $\leq 5 \times$ ULN (patient is asymptomatic)	
 
Repeat LFT within the next week
 
If elevation is confirmed, initiate close observation of the patient
 
	Investigator discretion Monitor LFT within 1 to 4 weeks
ALP (isolated)		

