$> 2 \times$ ULN (in the absence of known bone pathology)	
 
Repeat LFT within 48 hours
 
If elevation persists, establish causality
 
Complete liver CRF
 
	Investigator discretion Monitor LFT within 1 to 4 weeks or at next visit
TBL (isolated)		

Criteria	Actions required	Follow-up monitoring
> 2 × ULN (in the absence of known Gilbert syndrome)	
 
Repeat LFT within 48 hours
 
If elevation persists, discontinue the study drug immediately
 
Hospitalize if clinically appropriate
 
Establish causality
 
Complete liver CRF
 
	ALT, AST, TBL, Alb, PT/INR, ALP and γGT until resolution c (frequency at investigator discretion) Test for hemolysis (e.g., reticulocytes, haptoglobin, unconjugated [indirect] bilirubin)
> 1.5 to ≤ 2 × ULN (patient is asymptomatic)	
 
Repeat LFT within the next week
 
If elevation is confirmed, initiate close observation of the patient
 
	Investigator discretion Monitor LFT within 1 to 4 weeks or at next visit
Jaundice	
 
Discontinue the study treatment immediately
 
Hospitalize the patient
 
Establish causality
 
Complete liver CRF
 
	ALT, AST, TBL, Alb, PT/INR, ALP and γGT until resolution c (frequency at investigator discretion)
Any AE potentially indicative of a liver toxicity*	
 
Consider study treatment interruption or discontinuation
 
Hospitalization if clinically appropriate
 
Establish causality
 
Complete liver CRF
 
	Investigator discretion

aElevated ALT/AST > 3 × ULN and TBL > 2 × ULN but without notable increase in ALP to > 2 × ULN

b(General) malaise, fatigue, abdominal pain, nausea, or vomiting, or rash with eosinophilia

cResolution is defined as an outcome of one of the following: (1) return to baseline values, (2) stable values at three subsequent monitoring visits at least 2 weeks apart, (3) remain at elevated level after a maximum of 6 months, (4) liver transplantation, and (5) death.

[Chalasani and Regev 2016](#)

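### Tables 16-1 and 16-2 define a potential Hy's Law case differently; for a mainly unconjugated bilirubin rise, this decides whether treatment stops at once or a repeat test comes first

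*Protocol*

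**What the plan says.** **Definitions.** Protocol Table 16-1 lists potential Hy's Law cases among the liver events: ALT or AST above 3 x ULN with total bilirubin above 2 x ULN, qualified by "mainly conjugated fraction] without notable increase in ALP to" more than 2 x ULN. Footnote a of Table 16-2 reads: "Elevated ALT/AST > 3 × ULN and TBL > 2 × ULN but without notable increase in ALP to > 2 × ULN". It does not mention the fraction.

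**Actions.** Table 16-1 holds definitions only; all actions are in Table 16-2. For a potential Hy's Law case the instruction is "Discontinue the study treatment immediately". For asymptomatic ALT or AST above 3 and up to 5 x ULN it is "Repeat LFT within the next week". For bilirubin above 2 x ULN, under a heading that labels the rows as isolated bilirubin, it is "Repeat LFT within 48 hours" and then "If elevation persists, discontinue the study drug immediately".

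**Links.** Section 9.1.1 makes discontinuation mandatory for qualifying liver events and refers to Section 10.2.1 and to both tables. Section 10.2.1 sends the reader to Section 16.2 for the definitions, and both versions are there.

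**Tests.** The panel in Section 8.4.3.3 includes "aspartate aminotransferase (AST), total bilirubin (TBL), serum albumin (Alb") but no direct or conjugated bilirubin. Direct bilirubin appears in Section 10.2.1, for the confirmatory repeat: "Repeat liver chemistry tests (ALT, AST, TBL, Direct Bilirubin, PT/INR, ALP and" gamma-GT.

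**The concern.** A rule for mandatory discontinuation should give the same answer whichever page of the appendix is open. Here one row of Table 16-2 can be entered through either of two definitions, and no text says which prevails. Two sites could classify the same laboratory result differently: one would stop treatment, the other would keep the patient on treatment pending a repeat.

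The potential Hy's Law case is one of the most consequential liver categories in the appendix, and both the protocol (Section 12.4.1) and the SAP (Section 2.5.1) treat safety data as primary endpoints. The stricter definition also needs a measurement that the routine panel does not list, so a site trying to follow Table 16-1 may lack what it needs on the first result.

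**Working it through.** No sample size, power or event figure bears on this point. The check is a term-by-term comparison, followed by tracing the discordant patient through Table 16-2.

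**Step 1: the definitions side by side**

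| Element | Table 16-1 | Table 16-2, footnote a |
|---|---|---|
| ALT or AST | > 3 x ULN | > 3 x ULN |
| Total bilirubin | > 2 x ULN | > 2 x ULN |
| Bilirubin fraction | mainly conjugated | no condition |
| ALP | not above 2 x ULN | not above 2 x ULN |

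They differ in one element. They can disagree only when the first two limits are exceeded, ALP is not, and the bilirubin is not mainly conjugated.

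**Step 2: the discordant profile under footnote a.** It is a potential Hy's Law case, so treatment is discontinued immediately.

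**Step 3: the same profile under the Table 16-1 definition (no known Gilbert syndrome).** It is not a potential Hy's Law case, so the other Table 16-2 rows decide:

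- *ALT or AST > 8 x ULN (or > 500 U/L with an elevated baseline), or > 3 x ULN with the listed symptoms, or jaundice:* immediate discontinuation anyway. No conflict.
- *ALT or AST > 5 to 8 x ULN (or up to 500 U/L with an elevated baseline), none of the above:* the ALT/AST row gives a repeat within 48 hours, and discontinuation if the elevation lasts more than 2 weeks.
- *ALT or AST > 3 to 5 x ULN, asymptomatic:* the ALT/AST row gives a repeat within the next week and close observation if confirmed. It has no discontinuation step.
- *Bilirubin > 2 x ULN row, if it applies to a combined rise:* a repeat within 48 hours, and immediate discontinuation if it persists.

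Whether the last row applies is itself unclear. Its Table 16-2 heading restricts it to isolated bilirubin, and a combined ALT and bilirubin rise is not plainly isolated. Table 16-1, however, lists bilirubin > 2 x ULN as a liver event in its own right, without that restriction.

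**Step 4: an illustrative patient.** Assume no symptoms, ALT 4 x ULN, total bilirubin 2.5 x ULN mainly unconjugated, and normal ALP.

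| Route | First action |
|---|---|
| Footnote a | stop immediately |
| Table 16-1, bilirubin row applied | repeat within 48 hours; stop if it persists |
| Table 16-1, only the ALT/AST row applied | repeat within one week (7 days); observe if confirmed |

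**Step 5: can the fraction be known?** Section 8.4.3.3 lists total bilirubin only. Section 10.2.1 names direct bilirubin for the repeat. The bilirubin > 2 x ULN row of Table 16-2 mentions indirect bilirubin, but only as an example within a haemolysis work-up. On the protocol text, the fraction may therefore first become available at the repeat.

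**The case against.** The strongest reply is that Table 16-1 prescribes nothing. A reader might infer that the two tables order different actions; they do not. Every action is in Table 16-2, which carries its own definition in a footnote to the row concerned. An investigator working from that table alone gets one clear answer. This stands, and it means the conflict lies between two definitions feeding one action row. It does not remove the conflict, because Sections 9.1.1 and 10.2.1 send the reader to both tables without an order of precedence.

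A second reply is that if the fraction is unknown on the first result, footnote a is the only usable rule at that moment. That has some force. But the protocol does not say that footnote a governs until the fraction is known, and the laboratory may report the fraction earlier than the protocol shows.

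Third, other provisions limit the consequence. Section 9.1.1 requires discontinuation when the investigator judges an abnormal laboratory value to be a safety risk. Section 10.2.1 has elevations re-tested, with interruption considered once confirmed. Under Table 16-1 the patient remains a liver event in any case, through the separate bilirubin criterion.

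Fourth, few patients should be affected. Section 5.2 excludes suspected or confirmed Gilbert's syndrome, total bilirubin above 120% of ULN, and ALT or AST above 1.5 x ULN at screening, and Table 6-2 prohibits UGT1A1 inhibitors. These last two replies reduce the practical weight of the point; they do not make the definitions agree.

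**Conclusion.** The inconsistency is real, and both definitions are fully legible, so neither redaction nor table extraction explains it. For a mainly unconjugated rise meeting no other immediate-stop criterion, the choice of definition changes the first action from immediate discontinuation to a repeat test within 48 hours or within one week.

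Three stronger readings are tempting but not supported:

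- *That any such patient is re-tested only after a week, with up to 7 days of further dosing.* A week is the sole instruction only for asymptomatic ALT or AST above 3 and up to 5 x ULN, and only if the isolated-bilirubin heading is read as excluding a combined rise. Otherwise a 48-hour repeat applies, or an immediate stop on another criterion.
- *That the Table 16-1 definition cannot be applied on the first result.* The laboratory manual and Site Operations Manual were not available and may provide for direct bilirubin. The protocol supports only that the fraction may not be assessable.
- *That reported Hy's Law counts will change.* SAP Section 2.5.3 mentions liver and renal event tables and the use of the most extreme multiple of ULN per visit, but the visible text specifies no Hy's Law output or definition.

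The documents give no frequency for the profile, and none is assumed here. The conclusion rests on Section 9.1.1 citing both tables and on no visible text ranking them.

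**What to change.** In the next amendment the sponsor should:

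1. Reconcile Table 16-1 and footnote a of Table 16-2 to one definition of a potential Hy's Law case. Which one is a clinical decision for the sponsor.
2. State which Table 16-2 row governs a combined ALT/AST and bilirubin elevation that is not a potential Hy's Law case, and whether the isolated-bilirubin heading covers it.
3. Check that the tests in Section 8.4.3.3 allow the chosen definition to be applied. If a fraction condition is kept, list direct bilirubin there and say which row applies until the fraction is known.
4. Use the same definition for any liver-event tables produced under the SAP.

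The cost is a wording change in one appendix and a matching line in the SAP. If the fraction is needed and not already reported, it adds at most one assay on a blood sample already drawn.
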